4.2.2.7 Time from randomisation to second progression (PFS2)

PFS2 will be analysed using a stratified log-rank tests, using the same methodology as described for the primary PFS endpoint. The effect of durvalumab versus placebo will be estimated by the HR together with its corresponding 95% CI and p-value. KM plot will be presented by treatment arm. Summaries of the number and percentage of patients who have an event as well as those who were censored will be provided along with the medians for each treatment.

The number and percentage of patients experiencing a PFS2 event and the type of progression (Symptomatic progression, Objective radiological progression, Other) will also be summarised by treatment arm.

This analysis will be repeated on the ITT set.

4.2.2.8 Change in Tumour Size

Descriptive summaries of change in tumour size will also be presented for target lesion size and percentage change from baseline in target lesion size across all time points. Further, descriptive summaries of best percentage change from baseline in target lesion size will be presented, alongside a waterfall plot. Best change in target lesion size is defined as the maximum reduction of lesion size from baseline, or the minimum increase of lesion size from baseline in the absence of a reduction.

4.2.3 Patient-reported outcomes

Compliance rate

Summaries of the number of expected, received and evaluated questionnaires, as well as the compliance and evaluability rates will be presented by treatment arm at each visit (including baseline). The overall number of expected, received and evaluated questionnaires, as well as the compliance and evaluability rates over all time points will also be presented.

Symptom and HRQoL/function improvement rate

A summary of the symptom improvement rate for all symptom scales/items in EORTC QLQ-C30 and QLQ-LC13 will be produced. Similarly, a summary of function/HRQoL improvement rate for each of the 5 function scales (physical, role, emotional, cognitive, and social) and global health status/QoL will be produced.

Symptom and HRQoL/function improvement will be analysed by comparing the treatment arms using a logistic regression model adjusting for the stratification factors. The odds ratio (an odds ratio greater than 1 will favour durvalumab) together with its associated profile likelihood 95% CI and p-value (based on twice the change in log-likelihood resulting from the addition of a treatment factor to the model) will be obtained for each scale/item using the same method as done for ORR and will be presented graphically on a forest plot. If there are very few responses in one treatment arm, a Fisher's exact test will be considered.

Time to symptom and HRQoL/function deterioration

Time to symptom and function/HRQoL deterioration will be analysed for each of the symptom scales/items, function scales, and global health status/QoL in EORTC QLQ-C30 and QLQ-LC13. This will be achieved by comparing between treatment arms using a stratified log-rank test as described for the primary analysis of PFS. The HR and 95% CI for each scale/item will be presented graphically on a forest plot.

For each of the symptom scales/items, functional scales, and global health status/QoL, time to deterioration will be presented using a Kaplan-Meier plot. Summaries of the number and percentage of patients experiencing a clinically meaningful deterioration or death and the median time to deterioration will also be provided for each treatment arm.

Time to symptom and HRQoL/function deterioration will also be listed.

Change from baseline in key symptoms, HRQoL and functioning

Change from baseline in the 5 pre-specified symptoms, the physical functioning score and the overall health status score will be analysed using a linear mixed model for repeated measures (MMRM) analysis making use of all data from baseline up to 12 months. MMRM analysis will be of change from baseline in the scores for each assessment timepoint and the Bonferroni-Holm procedure ([Holm 1979](#)) for adjusting the significance level will be used to aid interpretation. The analysis will compare the average treatment effect from the point of randomisation until 12 months unless there is excessive missing data (defined as >75% missing data). The 5 key endpoints will be tested at a 1% significance level. Physical functioning score and overall health status score will also be analysed using similar methods, except they will be tested at the 5% significance level.

The MMRM model will include the fixed categorical effects of treatment, visit, and treatment-by-visit interaction, the level of PD-L1 expression (PD-L1<1% or PD-L1≥1%) and prior therapy (cCRT or sCRT) as well as the continuous fixed covariates of baseline score and baseline score-by-visit interaction. Restricted maximum likelihood (REML) estimation will be

used. An overall adjusted mean estimate will be derived that will estimate the average treatment effect over visits giving each visit equal weight. For this overall treatment comparison, adjusted mean estimates per treatment group and corresponding 95% CIs will be presented along with an estimate of the treatment difference, 95% CI, 99% CI (for the 5 key symptoms only) and p-value. An unstructured covariance matrix will be used to model the within-subject error and the Kenward-Roger approximation will be used to estimate the degrees of freedom. If the fit of the unstructured covariance structure fails to converge, the following covariance structures will be tried in order until convergence is reached: Toeplitz with heterogeneity, autoregressive with heterogeneity, Toeplitz, autoregressive and compound symmetry.

Multiple imputation techniques for missing values may be considered to explore the robustness of any treatment effect.

It is acknowledged that patients will discontinue treatment at different timepoints during the study and that this is an important time with regards to symptoms and HRQoL data collection. To account for this, and to include the discontinuation and follow up visits, a generic visit variable will be derived for each patient in order that the average treatment effect can be analysed using the above method. Each visit will be assigned a sequential number. The time from randomisation to each of these will be derived to select only those visits occurring within the first 12 months of randomisation.

As an example, say a patient X attends the first 4 scheduled visits of a 4-weekly schedule and then discontinues treatment, whilst patient Y discontinues treatment after the first scheduled visit, the first 6 generic visits would be as in [Table 10](#) below.

Table 10 Generic visit variable derivation example

Generic visit	Study day (week)	
	Patient X	Patient Y
Baseline	Baseline	Baseline
1	29	29
2	57	54 (discontinuation)
3	85	85
4	113	113
5	138 (discontinuation)	141
6	169	169

Summaries of original and change from baseline values of each symptom scale/item, the global HRQoL score, and each functional domain will be reported by assessment timepoint for each treatment arm. Graphical presentations may also be produced as appropriate.

Summaries of the number and percentage of patients in each response category at each assessment timepoint for each ordinal item (in terms of the proportion of patients in the categories of Improved, Stable, and Worsened as defined in [Table 7](#)) will also be produced for each treatment arm. For each of the visit level summaries of Improved/Worsened/Stable, all patients with a baseline and post-baseline score will be included, thus the denominator may differ from the time to worsening and improvement rate endpoints.

All EORTC QLQ-C30 and QLQ-LC13 raw scores and scale scores will be listed.

All PRO analyses described above below will be repeated on the ITT set.

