A summary of the symptom improvement rate for all symptom scales/items in EORTC QLQ-C30 and QLQ-LC13 will be produced. Similarly, a summary of function/HRQoL improvement rate for each of the 5 function scales (physical, role, emotional, cognitive, and social) and global health status/QoL will be produced.

Symptom improvement rates will be analysed by comparing between treatment arms using a logistic regression model. The odds ratio and 95% CI for each scale/item will be presented graphically on a forest plot. If there are very few responses in 1 treatment arm, a Fisher's exact test will be considered.

Change from baseline

Summaries of original and change from baseline values of each symptom scale/item, the global HRQoL score, and each functional domain will be reported by assessment timepoint for each treatment arm. Graphical presentations may also be produced as appropriate. Summaries of the number and percentage of participants in each response category at each assessment timepoint for each ordinal item (in terms of the proportion of participants in the categories of improvement, stable, and deterioration as defined in Table 12) will also be produced for each treatment arm.

EuroQol-5-Dimension 5-Level questionnaire

The change from Baseline in health state utility values and the visual analogue scale will be compared between treatment arms at each visit using a mixed model repeated measures analysis, which adjusts for the same factors as the primary analysis and also the baseline health state utility value/visual analogue scale as appropriate. Adjusted mean differences between treatments and 95% CIs from these analyses will be presented, but, as this analysis is exploratory in nature, p-values will not be calculated.

Descriptive statistics will be reported for the health state domain (eg, proportion in each domain) and the visual analogue scale by visit, as well as the change in the visual analogue scale value and the derived utility index value from Baseline. To support future economic evaluations, additional appropriate analyses may be undertaken, for example, mean health state utility pre- and post-treatment, and pre- and post-progression.

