1.3 Number of subjects

The study will randomise approximately 400 patients in the ITT population and approximately 375 patients in the mITT population. Patients who received prior concurrent chemoradiation (cCRT) or sequential chemoradiation (sCRT) and have not progressed following definitive chemoradiation therapy will be randomised in a 2:1 ratio to receive durvalumab and placebo.

Randomisation will be stratified by the level of PD-L1 expression (PD-L1 <1% or PD-L1 ≥1%) and prior therapy (cCRT or sCRT).

The number of patients with sensitizing epidermal growth factor receptor (EGFR) mutation or anaplastic lymphoma kinase (ALK) rearrangement randomised will be capped at approximately 7% of the total number of patients randomised. In order to reflect global clinical practice, study will recruit at least 60% of patients who received prior cCRT. The majority of patients will be recruited in China.

Eligible patients will be in complete response (CR), partial response (PR), or have stable disease (SD) following definitive, platinum-based, cCRT or sCRT.

The primary objective of this study is to assess the efficacy of durvalumab compared with placebo in terms of PFS per RECIST 1.1 as assessed by BICR in the mITT population. The key secondary endpoint (i.e., included in the multiple testing procedure) is OS (mITT).

The primary PFS (mITT) analysis data cut-off (DCO) will occur when whichever of the following conditions have been met first:

- Reaching approximately [CCI] BICR progression-free survival events across the durvalumab and placebo treatment arms (approximately [CCI] maturity) in the mITT population

OR

- Approximately [CCI] months follow-up from last patient randomized to the study.

If the true PFS HR is [CCI] with an estimated [CCI] BICR PFS events in the mITT, the study will provide at least [CCI] power to demonstrate a statistically significant difference for PFS with [CCI] this translates to approximately a [CCI]-month benefit in median PFS over [CCI] months on placebo. The smallest treatment difference that would be statistically significant is a HR of [CCI]. A recruitment period of approximately [CCI] months and a follow-up period of [CCI] months are expected for the PFS (mITT) final analysis.

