See Appendix A for further details on the derivation of the confirmation of deterioration, 2-missed visit rule and length of 2 missed visit window.

The population for the analysis of time to QoL/function deterioration/worsening will include patients who have baseline scores of ≥ 10 .

Symptom improvement rate (QLQ-C30 and QLQ-LC13)

The symptom improvement rate will be defined as the number (%) of patients with a minimum of 2 consecutive assessments at least 14 days apart that show a clinically meaningful improvement (a decrease in score of ≥ 10) in that symptom from baseline. Missed visits are not allowed in between consecutive assessments of improvement. This is considered a conservative approach whereby an improvement is considered a 'positive' outcome and therefore for any avoidance of doubt in the assessment of an improvement, missed visits are not allowed.

The denominator will consist of the subset patients who have a baseline symptom score of ≥ 10 .

HRQoL/function improvement rate (QLQ-C30)

The HRQoL/function improvement rate will be defined as the number (%) of patients with a minimum of 2 consecutive assessments at least 14 days apart that show a clinically meaningful improvement (an increase in score of ≥ 10) in that scale from baseline. Missed visits are not allowed in between consecutive assessments of improvement. This is considered a conservative approach whereby an improvement is considered a 'positive' outcome and therefore for any avoidance of doubt in the assessment of an improvement, missed visits are not allowed.

The denominator will consist of the subset of patients who have a baseline QoL/function score of ≤ 90 .

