- In all patients: Time from randomisation to the date of death or to the date of censoring for censored patients, regardless of treatment arm.

A sensitivity analysis will be performed to account for COVID-19 deaths. This analysis is a repeat of the primary OS analysis, but patients who died and the primary or secondary cause of death is due to confirmed/suspected COVID-19 infection, or a confirmed/suspected COVID-19 infection is reported as a fatal AE, are censored at their confirmed/suspected COVID-19 infection death date.

Subgroup analyses maybe performed if there is a sufficient number of OS events (≥ 20 events [≥ 10 events in each subgroup/treatment arm]). Subgroup analyses and a forest plot will be generated comparing OS between treatments in the same way as previously specified for PFS. This analysis will be repeated on the ITT set.

Cox proportional hazards modelling will be employed to assess the effect of pre-specified covariates on the HR estimate. The result from the model with and without additional covariates will be presented as specified for PFS.

Consistency of treatment effect between stratification factors will be analysed. Interactions between treatment and stratification factors will also be tested to rule out any qualitative interaction using the approach of Gail and Simon ([Gail and Simon 1985](#)), as previously specified for PFS.

4.2.2.2 **Proportion of patients alive at 12 months (OS12) and at 24 months (OS24)**

OS24 will be summarised (using the Kaplan-Meier curve) and presented by treatment arm along with 95% CI using the log-log transformation.

OS12 will be defined as the Kaplan-Meier estimate of OS at 12 months. The same analysis as for OS24 will be produced.

These analyses will be repeated on the ITT set.
Other landmarks may be summarised as appropriate.

4.2.2.3 **Objective response rate**

The ORR will be based on the programmatically derived RECIST 1.1 using the BICR tumour data, without the need for confirmation of the first documented response. The ORR will be

compared between durvalumab versus placebo using logistic regression models adjusting for the stratification factors as in the PFS analysis.

The results of the analysis will be presented in terms of an odds ratio (an odds ratio greater than 1 will favour the durvalumab arm) together with its associated profile likelihood 95% CI and p-value (based on twice the change in log-likelihood resulting from the addition of a treatment factor to the model). ^{CCI}

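### The PRO improvement-rate logistic models omit the baseline score, which costs some power and lets chance baseline imbalance move the odds ratios

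*SAP*

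**What the plan says.** SAP 4.2.3 specifies the improvement-rate analysis for every QLQ-C30 and QLQ-LC13 symptom scale or item, the five function scales and global health status: "Symptom and HRQoL/function improvement will be analysed by comparing the treatment arms using a logistic regression model adjusting for the stratification factors". The odds ratio, profile-likelihood interval and likelihood-ratio p-value are obtained "using the same method as done for ORR". The ORR section (SAP 4.2.2.3) has the arms "compared between durvalumab versus placebo using logistic regression models adjusting for the stratification factors as in the PFS analysis". SAP 1.3 identifies those factors: "Randomisation will be stratified by the level of PD-L1 expression" and by prior therapy (cCRT or sCRT). Protocol 9.5.1.9 names no covariates: "Symptom improvement rates will be analysed by comparing between treatment arms using a logistic regression model".

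Baseline score enters only through the denominators in SAP 3.2.3.1. For symptoms, "The denominator will consist of the subset patients who have a baseline symptom score of" at least 10. For function and QoL, patients count if they are those "who have a baseline QoL/function score of" at most 90.

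Elsewhere the SAP does adjust for baseline. The MMRM in the same section includes the stratification factors "as well as the continuous fixed covariates of baseline score and baseline score-by-visit interaction", and the EQ-5D-5L model (SAP 4.2.6.1) includes baseline utility or VAS. No section adds baseline score to the improvement models, even as a sensitivity analysis.

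**The concern.** Improvement means moving at least 10 points from the patient's own baseline at two or more consecutive assessments. Where the patient starts should therefore matter. Cough, chest pain and appetite loss, three of the five primary PRO symptoms, are single items with four response options (Protocol 8.1.4.1), so their scores can only be 0, 33, 67 or 100. A patient starting at 33 improves only by reaching 0. A patient at 67 has two improving levels, and a patient at 100 has three. The denominator rule removes those who cannot improve by 10 points but leaves this gradient among those who remain.

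Two things follow if the gradient is real. The unadjusted test loses power. And a chance difference in mean baseline between the 2:1 arms shifts the estimated odds ratio. The second matters for reading the forest plot, which shows more than 20 scales and items. Every patient in the denominator has a baseline score by definition, so adjusting for it loses no data.

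**Working it through.** **No figure to reproduce.** The documents give no sample size, response rate, effect size or power for the improvement rates. What follows is illustrative.

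**Inputs from the documents.** 2:1 allocation and about 375 mITT patients, hence about 250 and 125 (SAP 1.3); 2-sided testing with a likelihood-ratio p-value; PD-L1 level and prior therapy as covariates.

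**Assumed inputs.** A single four-level item; eligible baselines 33.3, 66.7 and 100 with probabilities 0.6, 0.3 and 0.1; conditional treatment odds ratio 2.0; evaluable N of 200, 300 or 375; and γ, the log-odds of improvement per 33.3-point baseline step, of 0, 0.5, 1.0 or 1.5. There were 1,500 simulated trials per power cell and 3,000 per null cell.

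**Power, planned model → model with baseline score (%)**

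| γ | N=200 | N=300 | N=375 |
|---|---|---|---|
| 0 | 65.0 → 65.3 | 81.3 → 80.9 | 89.0 → 88.8 |
| 0.5 | 60.7 → 61.5 | 77.9 → 79.7 | 85.5 → 86.5 |
| 1.0 | 54.4 → 59.6 | 71.3 → 74.9 | 79.7 → 83.8 |
| 1.5 | 46.4 → 53.9 | 63.0 → 70.8 | 72.6 → 81.9 |

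The gain is nil when baseline is unrelated to improvement, and about 1–2, 4–5 and 7–9 points as the dependence strengthens.

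**Chance imbalance at N=300.** In baseline steps, the mean is 0.3×1 + 0.1×2 = 0.5 and the variance is 0.3×1 + 0.1×4 − 0.5² = 0.45. The SD is therefore √0.45 × 33.3 ≈ 22.3 points. The SE of the between-arm difference is 22.3 × √(1/200 + 1/100) ≈ 2.7 points, which agrees with the simulated 2.7–2.8.

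| γ | OR multiplier at +1 SE, planned | at +2 SE, planned | at +1 SE, with baseline |
|---|---|---|---|
| 0.5 | 1.06 | 1.12 | 1.01 |
| 1.0 | 1.09 | 1.18 | 1.01 |
| 1.5 | 1.11 | 1.24 | 0.99 |

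The correlation of the estimated log odds ratio with the imbalance is 0.22–0.41 for the planned model and −0.02 to 0.05 with baseline added.

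**Type I error (N=300, no treatment effect).** Rejection is 5.1–6.1% for the planned model and 5.2–5.6% with baseline.

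**Non-collapsibility.** With a conditional odds ratio of 2.0 at N=300, the planned model's median estimate is 1.98, 1.88 and 1.80 for γ of 0.5, 1.0 and 1.5. The adjusted model gives 2.02–2.04.

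**A second set of assumptions.** N=220 with baseline at least 10, true odds ratio 2.2, the same three baseline levels (their mix also assumed), and 3,000 trials per scenario. Relative efficiency is (mean z adjusted ÷ mean z unadjusted)² − 1.

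| Control improvement at 33/67/100 | Power, unadjusted → adjusted | Equivalent extra patients |
|---|---|---|
| 25/40/50% | 73 → 73% | 4% |
| 20/45/65% | 66 → 70% | 11% |
| 15/50/75% | 55 → 64% | 23% |

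In the 15/50/75% case with no treatment effect, the log odds ratio moves by 0.93 per SD of baseline imbalance unadjusted and by −0.10 adjusted. A 0.2 SD imbalance is 0.2/0.144 ≈ 1.4 SE. It shifts the log odds ratio by 0.93 × 0.2 ≈ 0.19 (OR about 1.20) unadjusted, against −0.10 × 0.2 = −0.02 adjusted. The first set agrees: 0.2 SD at N=300 is 0.2/√(1/200 + 1/100) ≈ 1.6 SE, and 1.11 to the power 1.6 is about 1.19.

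**How often.** An imbalance of 1.4 SE or more in either direction has probability about 16%. Over somewhat more than 20 scales and items, that is about 3 or 4 of them, although correlated scores would tend to be imbalanced together.

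**The case against.** The planned test is valid over repeated randomisations, as the null rejection rates show. The imbalance effect is conditional, and the interval already covers it on average. With 147 and 73 patients and an assumed response of 30–50%, the SE of the log odds ratio is about 0.29–0.31, so a shift of 0.19 is about 0.6 SE. The main PRO inference is already baseline-adjusted: Protocol 9.5.1.9 makes the MMRM the primary PRO analysis, and improvement rates lie outside the alpha-controlled sequence of PFS and OS. The choice also follows a consistent convention, since ORR and time to deterioration adjust or stratify only by the randomisation factors. The gain depends on response rates nobody has documented and vanishes if baseline is unrelated to improvement. Finally, the Fisher's exact test that SAP 4.2.3 keeps for sparse responses cannot adjust for baseline.

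All of this stands as a limit on importance. None of it is a reason to leave the score out. The MMRM covers the five key symptoms, physical functioning and overall health status, but not the remaining scales. ORR has no baseline counterpart of the same measurement, so borrowing its model does not explain the omission here. When baseline was unrelated to improvement, adding it cost at most 0.4 percentage points of power in the simulations.

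**Conclusion.** The point holds. The improvement-rate models omit the baseline score, although the outcome is defined as change from it and the neighbouring PRO change models include it. The consequence is lost precision and sensitivity to chance imbalance, not inflated type I error. Under the assumed inputs the power loss is about 1 to 9 percentage points when baseline is prognostic. A one-SE imbalance moves the planned odds ratio by about 6 to 11% at N=300. The direction is secure if baseline predicts improvement, which the definition of the event makes likely; the size is illustrative. The primary and key secondary conclusions are unaffected, so this is a desirable improvement with medium confidence.

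**What to change.** In SAP 4.2.3, add the baseline score of the same scale or item as a continuous covariate to each improvement-rate logistic model, next to PD-L1 level and prior therapy, in both the mITT and ITT analyses. Keep the profile-likelihood interval and the likelihood-ratio p-value, with baseline in the models both with and without treatment. State that the odds ratio is conditional on baseline as well as on the stratification factors, because it will differ from the planned one even with perfect balance. State also that the Fisher fallback is unadjusted, and mark those scales on the forest plot.

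The cost is one term in the model statement and two sentences of text. No new data are needed and no patient is lost. Protocol 9.5.1.9 names no covariates, so it does not conflict. If the sponsor prefers to keep the planned model as the main one, the adjusted model should be pre-specified as a sensitivity analysis.
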